### **2.4.8 Analyses of quality of life (patient reported outcome)/health economics variables**

All of the analyses specified below will be done in mITT population. Observations collected after the initiation of the rescue therapy will be excluded from the analysis. Exploratory p-values will be provided, if applicable, from MMRM model described in [Section 2.4.5.1](#) for analyses of data from PAP.

#### ***Brief fatigue inventory***

The change from baseline up to Week 52 on severity and interference of fatigue as measured by BFI (individual questions as well as scale score) will be analyzed using the MMRM model described in [Section 2.4.5.1](#).

#### ***Brief Pain Inventory – Short Form (BPI-SF)***

The change from baseline up to Week 52 on severity (average of Questions 3, 4, 5, 6) and interference (Q9) of pain as measured by BPI-SF (individual questions as well as scale score) will be analyzed using the MMRM model described in [Section 2.4.5.1](#).

### ***SF-36***

The change from baseline up to Week 52 on 8 scales measured by SF-36 - physical functioning, role physical, bodily pain, mental health, role emotional, social functioning, vitality, and general health - as well as the 2 summary measures of physical health (PCS) and mental health (MCS) will be analyzed using the MMRM model described in [Section 2.4.5.1](#).

### ***Niemann-Pick B Health Assessment Questionnaire (NPB-HAQ)***

Three domains of NPB-HAQ – resource utilization, symptoms and physical activity - will be summarized separately with each question at each scheduled time point. For resource utilization, in the last three months of each scheduled time point, the following measures will be summarized: the number of physician visits (total number of physician visits by adding up all the visits from different specialists), the number of emergency room visits, the number of days of paid caregiver assistance and the number of DAYS of care/help from a family member(s) and/or friend(s). For symptom in the last three months of each scheduled time point, frequency and level of bothersome of each symptom will be listed. For physical activity in the last three months of each scheduled time point, the number and percentage of patients at each frequency of physical activities will be summarized.

### ***FACIT-Dyspnea***

The symptom scores have been discussed under secondary efficacy endpoints. Functional limitation scores will be provided in data listing.

### ***Health-related productivity***

Each question (about employment, household chores, homework/classes) will be summarized separately at each scheduled time point. At each scheduled time point, the following number of hours missed due to ASMD or its treatment will be summarized: the number of hours missed of work, the number of hours missed of house hold chores, the number of hours missed of homework or class. If the answer for ASMD or its treatment(s) keep you from work, house hold chores, homework or class is “no”, then number of hours missed will be imputed as 0 for the summary.

### ***EQ-5D-5L***

Each question on a 1-5 scale (for mobility, self-care, usual activities, pain/discomfort, anxiety/depression), higher score indicating worse, will be summarized separately at each scheduled time point, providing number and % of patients at each level. The change from baseline up to Week 52 on the VAS scale score on “your health today” (0 indicating the worst, and 100 indicating the best) will be analyzed using the MMRM model described in [Section 2.4.5.1](#).

### ***PGIS/PGIC***

For PGIC, 7 categories of response will be converted to the following numeric values:

- Very much Better = 3
- Moderately Better = 2

- A Little Better = 1
- No Change = 0
- A Little Worse = -1
- Moderately Worse = -2
- Very much Worse = -3

Observed numeric values at each post-baseline visits will be analyzed using MMRM model described in [Section 2.4.5.1](#). And in the MMRM model, the baseline value will be PGIS at screening with value of 0=none, 1=mild, 2=moderate, 3=severe, 4=very severe.

In addition, as supportive analysis, at week 52, patients will be categorized as responder if having numeric value of 3, 2, or 1, otherwise, patient will be categorized as non-responder if having numeric value of 0, -1, -2, -3 or missing. This binary measure of responder (yes vs no) at Week 52 will be analyzed with logistic regression including treatment and baseline as covariates.

The PGIS at baseline and post-baseline visits will be converted to a numeric score on 0-4 scale (0=none, 1=mild, 2=moderate, 3=severe, 4=very severe). Therefore, change from baseline at each post-baseline visits using MMRM model described in [Section 2.4.5.1](#).

#### **2.4.8.1 PAP+ETP quality of life analyses**

All of the quality of life endpoints throughout the study treatment epoch including all longitudinal time points from both PAP and ETP will be summarized by randomized treatment group in PAP, using mITT population. ANCOVA model with baseline and treatment group as covariates will be used to assess the means of each treatment group and the 95% CIs of both treatment groups as well as the difference between two groups at each time point. It is understood that all patients in ETP are on olipudase alfa.

## **2.5 PATIENT NARRATIVES**

Patient narratives criteria for this study are as follows:

- Deaths
- Serious adverse event
- Adverse Events leading to permanent treatment discontinuation
- Adverse events of special interest including the followings:
  - Protocol defined IARs (as specified in [Section 2.1.5.1](#))
  - Pregnancy of female patient or partner of a male patient
  - Symptomatic overdose of study drug
  - Any increase in AST, ALT, total bilirubin, or AP >3x baseline (prior to olipudase alfa therapy) and > ULN

- Any increase in total bilirubin or AP >1.5x baseline in the presence of AST or ALT >2x ULN
- Any increase in ALT or AST >3x the ULN combined with an increase in ALT or AST >2x baseline (prior to olipudase alfa therapy) with symptoms of fatigue, nausea, vomiting, right upper quadrant pain or tenderness (for adults only), fever, rash, or eosinophilia (> ULN)

Patients who meet these criteria will be listed and provided to the medical writer.

## 2.6 DATA HANDLING CONVENTIONS

### 2.6.1 General conventions

In general, the baseline value is defined as latest value prior to the start of first infusion, except for hematology parameters and possibly ECG parameters. For hematology parameters, the baseline value is defined as the average of all available values before the start of first infusion. Other exception may be the ECG parameters - Day 1/Week 0 (the first infusion visit) collects ECG in triplicate before the infusion; if 2 or more than 2 of these triplicate collections of ECG are before the first infusion, the average of these ECG parameter results will be considered as the baseline value; otherwise, the baseline value of ECG parameters will be taken from the latest observation before the first infusion.

Age at ASMD diagnosis = number of years between the date of birth and the date of ASMD diagnosis.

### 2.6.2 Missing data

In general, no imputation is planned for missing data. The following approaches are default methods for missing data handling. Some exploratory analyses can be planned with different strategies for treating missing outcomes.

- Categorical data at baseline will be summarized using counts (n) and percentages (%). The number of patients with missing data may be mentioned, but will not be included in the denominator for the calculation of percentages unless otherwise specified. When relevant, the number of patients with missing data is presented.
- Continuous data: The analyses and summaries for variables with continuous scales will be based on observed data only.

#### ***Handling of computation of treatment duration if investigational medicinal product end of treatment date is missing***

For the calculation of the treatment duration, the date of the last dose of study treatment is reported on the last infusion page in the eCRF.

### ***Handling of medication missing/partial dates***

No imputation of medication start/end dates or times will be performed. If a medication date or time is missing or partially missing and it cannot be determined whether it was taken prior to the start of first infusion or concomitantly with study, it will be considered a prior as well as a concomitant medication.

### ***Handling of adverse events with missing data***

- If the AE is missing start date and/or time, the treatment-emergent adverse event will be determined by the following conservative principle: An adverse event will be considered a treatment-emergent adverse event if it cannot be confirmed that the event is not a treatment-emergent adverse event due to missing data. Further, if the PAP or ETP period could not be determined, this AE will be considered as TEAE in PAP.
- If the timing of AE with respect to infusion start and/or end time could not be determined unambiguously, the AE will be assumed to be an algorithm-defined IAR.
- If the assessment of the relationship is missing, then the relationship of possibly related is assumed for the summary table, but no imputation will be done at the data level.
- If the worst severity grade is missing, a missing category will be added in the summary table.

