During the PAP, one rechallenge each will be allowed for doses administered at Week 0 (0.1 mg/kg olipudase alfa or placebo) and at Week 4 (0.3 mg/kg olipudase alfa or placebo). Patients who are unable to tolerate the rechallenge at those doses will be discontinued from the study. If a patient is discontinued due to inability to tolerate rechallenge (ie, a second dose of 0.3 mg/kg olipudase alfa), then an additional patient may be randomized. Any patient who successfully dose-escalates through Week 4, but cannot tolerate study drug infusions at later weeks, will continue in the trial at the Week 4 dose (ie, 0.3 mg/kg olipudase alfa or placebo) until end of study; likewise, any patient unable to tolerate a dose administered during later weeks will receive the HTD even if that dose is less than the target randomized dose and will continue in the ETP at this dose. The minimum active dose administered will be 0.3 mg/kg olipudase alfa.

During the ETP, the same dose-escalation conditions will apply for patients who cross over from the placebo arm during the PAP to the active treatment arm, except that patients unable to tolerate the rechallenge allowed each at Week 54 (0.1 mg/kg olipudase alfa) and at Week 58 (0.3 mg/kg olipudase alfa) will discontinue from the study and will not be replaced.

During the PAP and ETP, in-patient hospitalization will be required preinfusion and for at least 24 hours after the infusion during dose escalation (ie, through Week 16 and Week 70, respectively) and may be required at the quarterly and yearly visits up through the end of Year 2; in-patient hospitalization may be necessary during quarterly and yearly study visits in Years 3 through 5. For all other infusions, patients will be monitored for safety in the clinic for at least 1 hour. All patients will have an end of study/early discontinuation visit within 2 weeks after the last infusion of study treatment. In addition, all patients will receive a follow-up phone call for safety approximately 30 to 37 days after the last infusion of study drug.

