### 1.1 STUDY DESIGN AND RANDOMIZATION

This Phase 2/3, multicenter, repeat-dose, clinical trial will be divided into 2 consecutive major periods: 1) a randomized placebo-controlled, double-blind PAP from Day -60 to Week 52 to be followed by 2) an ETP. Initially, the ETP will be double-blind as patients in the placebo arm cross over to active treatment. Study drug will be defined during the PAP as olipudase alfa or placebo, and during the ETP as olipudase alfa, and will be administered intravenously once every 2 weeks for 52 weeks in PAP, then for ETP. Day -60 to -1 is part of screening period with no study drug; some of the screening assessments which are not repeated right before the first infusion of study drug on Day 1 serve as baseline value for the study.

After completing the PAP, patients will enter the ETP of the study. Those who were randomized to the active arm will continue receiving the dose they were receiving at the completion of the PAP. Patients randomized to the placebo arm in the PAP will cross over to active treatment in the first infusion in ETP and will undergo dose escalation to a target dose of 3.0 mg/kg olipudase alfa.

For treatment periods during the PAP and the ETP, dose-limiting toxicity (DLT) criteria (protocol Section 8.1.4) and study stopping rules (protocol Section 8.1.5) will apply. If a patient satisfies protocol-specified criteria of rescue therapy (protocol Section 8.1.6), the individual treatment blind will be broken and the patient if on placebo will be switched to olipudase alfa; for patients already on olipudase alfa, the treatment will continue unless the patient drops out of study.

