### ***Observation period***

The observation period will be divided into epochs:

- The **screening** epoch (or pretreatment epoch) is defined as the time from the signed informed consent date up to the start of the first infusion of investigational medicinal product (IMP) in the study (excluded).
- The **treatment** epoch is defined as the time from the first infusion of IMP (included) to the end of the study.
  - The treatment epoch for PAP is defined as the time from the first infusion of IMP (included) to:
    1. the time just prior to first infusion in ETP if the patient has an infusion in ETP;
    2. the last date the data are available if the patient has no infusion in ETP.
  - The treatment epoch for ETP is defined as the time from the first infusion in ETP to the end of the study.

Based on these epochs the safety data collected in this study will be classified as pre-treatment and treatment emergent.

The on-study observation period is defined as the time within treatment epoch.

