### **2.1.5.1 Adverse events variables**

#### ***Adverse event observation period***

- Pretreatment adverse events are adverse events (AEs) that started before the first administration of IMP.
- Treatment-emergent adverse events are adverse events that developed or worsened or became serious during the treatment epoch. These will be defined separately for PAP and ETP.

If due to incomplete information on AE start date/time, the period designation cannot be made unambiguously (for imputation of missing or incomplete dates, please refer to [Section 2.6.2](#)), the AE is assumed to be treatment-emergent (and treatment-emergent in PAP, if so required for assumption).

All adverse events (including serious adverse events and adverse events of special interest) will be coded to a lower-level term (LLT), preferred term (PT), high-level term (HLT), high-level group term (HLGT), and associated primary system organ class (SOC) using Medical Dictionary for Regulatory Activities (MedDRA).

Adverse events are collected from the time of signed informed consent until the end of the study.

Adverse events of special interest include:

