#### **Infusion associated reactions**

Protocol-defined infusion associated reactions (IAR): Any AE that occurs during the infusion or within up to 24 h after the start of the infusion and is considered related or possibly related to study treatment as judged by the investigator or the sponsor is defined as a protocol-defined IAR. An event occurring  $\geq 24$  h after the start of an infusion may be judged an IAR at the discretion of the investigator or sponsor. Sponsor identification will reconcile with investigator identification of IAR before the database lock as much as possible. It is, however, possible that the sponsor identifies an AE as an IAR which the investigator did not agree to be an IAR; in that case, the sponsor decision is deemed final.

For this study, IARs may present as hypersensitivity reactions, acute phase reactions (APR), and cytokine release syndrome (CRS).

IARs, specifically APRs and some hypersensitive reactions may be associated with changes in specific clinical laboratory parameters (see Section 10.4.1.3 of the study protocol), and will be reconciled with investigator identification of those events as marked in the AE log as appropriate, facilitated by periodic clinical/safety review of AEs.

Algorithm-defined IAR: All AEs that start between the start of infusion and the end of infusion plus 24 hours are defined as algorithm-defined IARs, irrespective of the perceived relation with study treatment. Any TEAEs with missing time but which happened on the same day or the day after the infusion will be considered as algorithm-defined IARs.

Pregnancy: Pregnancy of a female patient enrolled in the study as well as pregnancy occurring in female partner of a male patient enrolled in this study is captured as an adverse event of special interest. The eCRF provides urine pregnancy test results as positive or negative. Labs provide serum pregnancy test results. Pregnancy is entered in the database as an AE, and will be counted from the AE page.

Symptomatic overdose: This is captured as an adverse event in this study, and will be reconciled with the clinical review of dosing data. For details, please see Section 10.4.1.3 in the protocol. This will be counted from the AE page.

Laboratory values: The following laboratory values and symptoms will be considered AESIs:

- Any increase in AST, ALT, total bilirubin, or AP >3x baseline (prior to olipudase alfa therapy) and > ULN

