##### **2.4.6.1 Adverse events**

Pre-treatment adverse events are defined as those that have an onset date/time before the first infusion date/time of the patient. Treatment emergent adverse events are those that have an onset date/time in the treatment epoch. Any AE reported in the database with onset date after the end of the treatment epoch will be classified as post-treatment.

The epochs for safety analysis have been defined in [Section 2.1.5](#). Treatment-emergent adverse events will be presented for different periods under different treatment groups as follows (and as appropriate):

1. Adverse events started in PAP treatment epoch, by randomized treatment group.
2. Adverse events started in either PAP or in ETP while taking olipudase alfa. This will be presented by randomized treatment group as well as combined (ie, all patients treated with olipudase alfa).

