### ***Generalities***

The primary focus of adverse event reporting will be on treatment-emergent adverse events. Pretreatment adverse events will be described separately.

If an adverse event date/time of onset (occurrence, worsening, or becoming serious) is incomplete, an imputation algorithm will be used to classify the adverse event as pretreatment, or treatment-emergent. The algorithm for imputing date/time of onset will be conservative and will classify an adverse event as treatment emergent unless there is definitive information to determine it is pretreatment. Details on classification of adverse events with missing or partial onset dates are provided in [Section 2.6.2](#). If an AE worsens in severity, two AEs of same verbatim but with different start/end dates and different severity are captured separately on the AE log page in the eCRF.

The AE log page in the eCRF captures the date when the event become serious. If and when this date is non-missing, it indicates that the AE started as non-serious and became serious at a later date. To account for non-serious and serious parts of the AE collected in one AE log page, this AE will be split into two AEs – one non-serious, and one serious AE – with the same AE number, with the following modifications in data for these two AEs:

- Non-serious AE: AE end date, AE outcome, date of death or hospitalization, autopsy information, criterion for serious adverse event (SAE) will be blank.
- Serious AE: AE start date will use the date the event became serious.

Action taken towards study drug and action taken toward AE will be considered in relation to the date the event became serious, the last infusion date and dosing information, and a determination will be made, in consultation with safety monitor of the trial, as to whether the recorded fields belong to non-serious AE or serious AE; then the decision will be implemented in analysis. Any such decision will be rationalized in the CSR.

The adverse events summary will be presented by SOC and PT sorted by the internationally agreed SOC order and decreasing frequency of PTs within SOCs within the olipudase alfa treatment arm, unless otherwise specified. Multiple occurrences of the same event in the same patient will be counted only once in the tables within a particular treatment phase. The denominator for computation of percentages is the safety population within each treatment group.

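### An untimed adverse event on the day of the first ETP infusion defaults to the PAP, so in a crossed-over placebo patient a possible olipudase alfa event is counted under placebo and left out of the olipudase-exposure summaries

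*SAP*

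**What the plan says.** SAP 2.6.2, on adverse events with missing data, first treats an event as treatment-emergent unless it can be shown not to be. It then adds: "Further, if the PAP or ETP period could not be determined, this AE will be considered as TEAE in PAP". SAP 2.1.5.1 has the same default for incomplete start dates or times: "the AE is assumed to be treatment-emergent (and treatment-emergent in PAP, if so required for assumption". Neither distinguishes between randomized arms.

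The boundary between the periods is set in SAP 2.1.5. For a patient who continues, the PAP treatment epoch ends at "the time just prior to first infusion in ETP if the patient has an infusion in ETP". SAP 1.1 says what happens at that infusion: "Patients randomized to the placebo arm in the PAP will cross over to active treatment in the first infusion in ETP". Protocol 6.1 identifies it as the Week 54 infusion, in its text on "patients unable to tolerate the rechallenge allowed each at Week 54 (0.1 mg/kg olipudase alfa").

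The first PAP display in SAP 2.4.6.1 is "Adverse events started in PAP treatment epoch, by randomized treatment group". The second covers events that began while the patient was on olipudase alfa. For the previous-placebo group, SAP 2.4.6.14 restricts adverse-event summaries to olipudase alfa exposure in the ETP.

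A separate rule in SAP 2.1.5.1 covers untimed events near an infusion: "Any TEAEs with missing time but which happened on the same day or the day after the infusion will be considered as algorithm-defined IARs". SAP 2.6.2 likewise assumes an algorithm-defined IAR when timing relative to the infusion is ambiguous. SAP 2.4.6.1.2 tabulates algorithm-defined IARs for the PAP.

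**The concern.** For a patient randomized to olipudase alfa, the choice between PAP and ETP does not change the drug to which an event is attributed. For a placebo patient it does: the PAP is placebo and the ETP is drug. An unconditional PAP default therefore sends a possible first-exposure event to the placebo column.

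The Week 54 infusion day matters most, because the period boundary falls within it and a missing clock time alone makes the period undeterminable. First exposure to this enzyme is also where reactions are of particular interest: Protocol section 4 describes first-dose toxicity in the Phase 1 study.

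Two outputs are at stake. One is the controlled PAP table, including the list of most common events, which under SAP 2.4.6.1.1 requires a higher percentage on olipudase alfa than on placebo. The other is the set of summaries of events under olipudase alfa exposure. SAP section 2 says the PAP database will already hold ETP evaluations for most patients, so the PAP report is affected as well as the final one.

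**Working it through.** The plan states no figure on this point, so there is nothing to reproduce. The check is a trace through the rules, followed by simple proportions.

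**Trace of one event.** Take a placebo patient not rescued in the PAP, with an event dated on the Week 54 infusion day, no start time and no other information that places it.

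1. *Period.* The PAP ends just before that infusion (SAP 2.1.5). Without a time, the event could lie on either side, so the default in SAP 2.6.2 and 2.1.5.1 assigns it to the PAP.
2. *Column.* PAP events are shown by randomized group (SAP 2.4.6.1) or by treatment received in the PAP (SAP 2.3.2 and 2.4.6). For this patient both mean placebo.
3. *IAR status.* Under SAP 2.1.5.1 and 2.6.2 the event is an algorithm-defined IAR, so it can enter the PAP table of such reactions under placebo.
4. *Olipudase summaries.* Assigned to the PAP, it is absent from the on-olipudase display in SAP 2.4.6.1 and from the previous-placebo and overall groups in SAP 2.4.6.14.

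Steps 1 and 3 conflict. The IAR rule ties the event to the infusion, while the period rule places it before that infusion.

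**What is not affected.** An untimed event dated the day after the infusion is clearly in the ETP. A placebo patient rescued in the PAP already counts as olipudase alfa in the safety population (SAP 2.3.2).

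**Size.** About 36 patients are randomized 1:1 (SAP 1.4), so 36/2 = 18 per arm.

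- Placebo PAP column: up by at most 1/18 = 5.6 points per affected patient.
- Previous-placebo olipudase column: down by at most 1/18 = 5.6 points, taking all 18 as the denominator.
- Overall olipudase column: down by at most 1/36 = 2.8 points.

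These are ceilings. SAP 2.4.6.1 counts a patient once per event within a treatment phase, so nothing moves in a column where the patient already has that term.

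**Direction in the controlled comparison (assumed counts, for illustration).** Suppose the correctly placed counts for a term are 2/18 (11.1%) on olipudase alfa and 1/18 (5.6%) on placebo. The term qualifies as most common.

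- One further placebo patient's event is moved into the PAP: 2/18 v 2/18. The term drops off the list.
- Instead, one unclear event that arose in the ETP in an olipudase patient is moved into the PAP: 3/18 (16.7%) v 1/18 (5.6%). The gap widens from 5.6 to 11.1 points, against the drug.
- Both happen: 3/18 v 2/18, a gap of 5.6 points, as at the start.

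The sign depends on counts that the documents cannot supply. In the olipudase-exposure summaries no such offset exists for the previous-placebo group: an event can be lost from that column but not gained.

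**The case against.** Four counter-arguments have weight.

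*The default is the same for both arms.* This stands. A reader might infer that the rule biases the controlled comparison in one direction, in favour of the drug. The documents do not support that, because unclear events in olipudase patients are also drawn into the PAP.

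*The plan does not call this step conservative.* This also stands. A reader might take "The algorithm for imputing date/time of onset will be conservative" in SAP 2.4.6.1 as a claim about PAP versus ETP. The rest of that sentence concerns pretreatment versus treatment-emergent events. In SAP 2.6.2 the conservative principle likewise governs that question, and the period default follows as an addition.

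*Most Week 54 reactions can be placed.* Largely right. Patients are in hospital before the infusion and for at least 24 hours afterwards (Protocol 6.1). Investigators mark IARs in the eCRF (Protocol 10.4.1.3), and IARs are notified within 24 hours (Protocol 10.4.4.1). Sponsor and investigator reconcile them before lock (SAP 2.1.5.1), and protocol-defined IARs receive narratives (SAP 2.5). A protocol-defined IAR to the Week 54 infusion cannot have started before it. It would be wrong to infer that first-dose reactions in general are lost. What remains is untimed events that are not flagged, and partial dates. The SAP does not, however, say that an IAR flag overrides the default.

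*Safety analysis is descriptive.* True (SAP 2.4.6), which limits the consequence. It does not make the column assignment right or remove the conflict with the IAR rule.

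**Conclusion.** The point holds in a limited form. The period default puts an untimed event on the day of the first ETP infusion on the wrong side of the boundary relative to the SAP's own IAR rule. In a non-rescued placebo patient it records a possible olipudase alfa event as a placebo event.

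For the olipudase-exposure summaries the error can only reduce the previous-placebo count. For the controlled PAP comparison no net direction is established.

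The effect is at most 5.6 points per affected patient in the placebo or previous-placebo column and 2.8 points overall, and only where the patient has no other occurrence of the term in that column. This assumes 18 patients per arm, all placebo patients entering the ETP; with fewer in a column the step is one over that number. The number of affected events cannot be read from the documents. Given the inpatient stay and IAR reporting, it is probably small.

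A stricter remedy might seem natural: sending every unclear event to whichever period was on drug. That would keep all unclear olipudase events in the PAP while removing all unclear placebo events, true placebo events included, and so would build a differential bias into the controlled comparison.

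**What to change.** Add the same sentence, for both arms, to SAP 2.6.2 and 2.1.5.1: *An AE dated on the day of the first ETP infusion with missing start time, or identified as an IAR to that infusion, is assigned to the ETP.*

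For events whose dates are too incomplete to place, keep the PAP default in the controlled comparison. Where such an event occurs in a crossed-over placebo patient, also include it in the olipudase-exposure summaries, or show it there as a sensitivity count. Footnote the number of events placed by rule in each arm.

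The cost is one sentence in two places, a small change to the derivation and a footnote. No efficacy analysis is touched. The downside is a few more events in the olipudase-exposure columns and an occasional Week 54 event that truly preceded the infusion being placed in the ETP.
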